**Columbia University Medical Center**  
**Herbert Irving Comprehensive Cancer Center**  
**Version Date: 04/21/2021**

these events, we impose a minimum of 2 weeks of observation between consecutive patients. Patients who discontinue treatment because of progression of disease or death unrelated to treatment without experiencing a DLT will be censored at the time of their last DLT assessment and included up to the point of their last assessment. If the last assessment occurs prior to the 4 week DLT assessment, that is, prior to the end of the first cycle of treatment, the patient will be replenished. To the contrary, if the last assessment occurs 4 weeks or after, that is, after the end of the first cycle of treatment assessment and the patient received at least 80% of the planned doses of Sirolimus and Turalio® the patient will not be replenished. Upon Daiichi Sankyo's request, CUMC will provide updates for the total number of patients enrolled in the study.

[figure not shown]
The TITE-CRM with an empiric dose-toxicity model, a linear weight function and a normal prior distribution on the parameter with mean 0 and variance of 1.34 is used. The dose-toxicity model is calibrated such that the method will eventually select a dose that yields between 18% and 32% DLT (31, 32). The design does not allow for dose skipping or dose escalation immediately after a DLT is observed (33). The performance of the TITE-CRM is assessed under five potential scenarios with scenarios 3 and 4 being the most likely. The operating characteristics of our design given 2000 simulations are displayed in Table 2. With 18 patients, the design selects the correct MTD with probabilities over 53% for all scenarios. The scenarios were selected to have neighboring doses with DLT rates within 15% of the MTD rate. If the neighboring doses have DLT rates significantly different from the target of 25%, the probability of correct selection will be improved. Likewise, if the neighboring doses have DLT rates very similar to the target rate, the probability of correct selection will worsen.

| Doses of Sirolimus
Doses of Turalio®
Dose Level | 2mg
600mg
1 | 2mg
800mg
2 | 2mg
1000mg
3 | 4mg
1000mg
4 | 6mg
1000mg
5 |
|---|-------------------|-------------------|--------------------|--------------------|--------------------|
| Scenario 1  |                   |                   |                    |                    |                    |

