#### **4.2 Dose Limiting Toxicities for Phase I**

All patients who receive at least one dose of both study drugs will be evaluable for toxicity.

In order for a patient to be evaluable for DLT assessments, the patient must either incur a DLT during the DLT evaluation period or have received at least 80% of the planned doses of Sirolimus and Turalio®. Patients who do not fulfill one of these criteria should be considered non-evaluable for DLT assessment purposes, and be replaced.

A DLT is defined as an AE assessed as being possibly, probably, or definitely related to study drug administration that is:

- Not due to the underlying malignancy;
- Has no clear evidence of an alternative etiology; and
- Meets one of the following CTCAE v.4.03 criteria during the first 56 days of Turalio® and Sirolimus administration:
  - Any Grade  $\geq 4$  hematologic toxicity except grade 4 lymphopenia
  - Grade 3 neutropenia with fever
  - Grade 3 thrombocytopenia with clinically significant bleeding
  - Any circumstance that results in dose reduction.
  - Any Grade  $\geq 3$  non-hematologic toxicity except:
    - Nausea, vomiting, and/or diarrhea of Grade 3 severity that resolves within 3 days with optimal prophylaxis and/or treatment.
    - Grade 3 fatigue that resolves to Grade  $\leq 2$  within 2 days.
    - Grade  $\geq 3$  alkaline phosphatase that is related to underlying malignancy (eg, bone metastasis)
    - For hypercholesterolemia, hypertriglyceridemia, and hyperglycemia if unresolved after appropriate treatment with standard of care.

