### **8. DOSING DELAYS/DOSE MODIFICATIONS**

#### **8.1 Phase 1 Dose Modification**

All patients may have dose modifications at any time. During Cycle 1 in the phase 1 portion, however, the DLT must be recorded for safety purposes prior to dose reduction. Patients may have drug held for any reason for up to 14 days before discontinuing study treatment. Refer to Tables 4 - 7 below for specific dose modification instructions.

Patients will undergo therapeutic monitoring with trough levels of Sirolimus on day 2 of cycle 1 before receiving daily dose of Sirolimus on day 2 (+2 day window), day 8, day 15, and day 22 of Cycle 1, on day 1 of each subsequent cycle, unless clinically indicated, and during the End-of-Study visit. Trough levels may be measured at other time points as clinically indicated. As levels  $>18.0\mu\text{g}/\text{L}$  are more likely to be associated with an adverse events, dosing of Sirolimus will be held and/or reduced in the case of trough levels  $>18.0\mu\text{g}/\text{L}$  as indicated in the dose modification table (Table 4). Deviation of this dose modification can be done at the discretion of the treating investigator in discussion with the study principal investigator.

| Sirolimus Monitoring and Dose Modification |   |
|---|---|

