For suspected cases of cholestatic liver injury (eg, aminotransferase increase concurrent with hyperbilirubinemia, or liver biopsy suggesting cholestasis and/or ductopenia), patients will be followed to assess long-term outcome. Additional diagnostic and follow-up procedures might be implemented as appropriate to fully assess the event.

8.1.1.2 **Nausea and Vomiting** – Turalio® may be associated with nausea and/or emesis that can arise early in the course of therapy. Sirolimus may also contribute to nausea and emesis and may be held as well at the discretion of the treating physician.

| Nausea and Vomiting |   |
|----------------------------|---|
| Grade 3                    | Hold Turalio® dosing until improved to grade 1 or baseline. If delay <48 hours from start of maximal supportive treatment, then restart at cohort with next lower dose for Turalio®.

If delay for ≥48 hours despite maximal supportive treatment, discontinue study treatment. |
| Grade 4                    | If any grade 4 toxicity despite maximal supportive treatment, discontinue study treatment.  |

**Table 7.** Nausea and emesis dose modification recommendations

8.1.1.3 **Hyperglycemia** – immunosuppressive agents, including Sirolimus have been associated with hyperglycemia that responds to treatment.

| Hyperglycemia – Assessed by Fasting Blood Glucose and NOT CTCAE grades  |   |
|--|---|
| Grade 1 = 140-199 mg/dL  | Maintain Turalio® and Sirolimus dosing and institute diet modifications. Address any underlying contributing factors (infection, steroids) and consider initiating blood glucose lowering therapy.  |
| Grade 2 = 200-249 mg/dL  | Maintain Turalio® and Sirolimus dosing and initiate blood glucose lowering therapy.   |
| Grade 3 = 250-399 mg/dL  | Hold only Sirolimus dosing until improved to ≤ Grade 1. 
 
• If ≤7 days, dose reduction is at discretion of treating physician.
 
• If >7 days, dose reduce to cohort with next lower dose of Sirolimus.
 
 |
| Grade 4 = 400 mg/dL or higher

OR

Any hyperglycemia leading to diabetic ketoacidosis, hyperosmolar nonketotic | Discontinue from study drug treatment.  |

|   |  |
|---|--|
| coma, or requiring IV insulin infusion. |  |
|---|--|

**Table 8.** Hyperglycemia dose modification recommendations

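### Section 4.2's last DLT exemption is worded in reverse: a Grade 3 or higher lipid or glucose event is excused if unresolved and counted if controlled

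*Combined protocol and SAP*

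**What the plan says.** Section 4.2 defines a DLT as a related event within the first 56 days that meets one of several criteria. Two matter here.

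- Any non-hematologic toxicity of Grade 3 or higher is a DLT, with four exemptions listed beneath. The first is "Nausea, vomiting, and/or diarrhea of Grade 3 severity that resolves within 3 days with optimal prophylaxis and/or treatment". The second excuses Grade 3 fatigue that improves within 2 days. The third excuses alkaline phosphatase elevation caused by the malignancy. The fourth is "For hypercholesterolemia, hypertriglyceridemia, and hyperglycemia if unresolved after appropriate treatment with standard of care".
- Separately, "Any circumstance that results in dose reduction" is a DLT.

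Evaluability requires either a DLT or at least 80% of planned doses of both drugs. Otherwise, "Patients who do not fulfill one of these criteria should be considered non-evaluable for DLT assessment purposes, and be replaced".

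Management in Section 8.1:

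- "Patients may have drug held for any reason for up to 14 days before discontinuing study treatment".
- Table 8, headed "Assessed by Fasting Blood Glucose and NOT CTCAE grades", holds sirolimus alone for Grade 3 hyperglycemia until improvement. Reduction is optional after 7 days or less and required after more than 7 days. Grade 4 goes straight to discontinuation.
- Table 9 interrupts treatment for Grade 3 or 4 non-hematologic events until recovery, then resumes one dose level lower.

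Section 13.3.1 reports DLT proportions by dose level and the final model estimates. Section 9.7 says the continual reassessment method identified dose level 3 as the Phase 2 dose.

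**The concern.** An exemption should excuse events that treatment can manage. This one excuses those it cannot. A reader applying the text literally would score an uncontrolled Grade 3 triglyceride elevation as no DLT and a controlled one as a DLT.

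The DLT classification is the outcome behind the Phase 1 primary objective, the 25% target and the Section 13.3.1 estimates. Errors could go either way: missing unresolved events lowers the estimated DLT rate, and counting controlled ones raises it. For glucose the second may be the more common, since Section 8.1.1.3 says agents such as sirolimus "have been associated with hyperglycemia that responds to treatment". Section 9.1.2 lists hypertriglyceridemia and hypercholesterolemia among sirolimus effects seen in at least 30% of patients, grade not given, so lipid events were foreseeable in Phase 1.

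**Working it through.** **Direction of the rule.** Under the Grade 3 or higher non-hematologic criterion, an event is a DLT if no exemption applies.

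| Event | Resolves on treatment | Does not resolve |
|---|---|---|
| Grade 3 nausea, vomiting, diarrhea (within 3 days) | exempt | DLT |
| Grade 3 fatigue (within 2 days) | exempt | DLT |
| Lipids and glucose, as printed | DLT | exempt |
| Lipids and glucose, reworded | exempt | DLT |

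The alkaline phosphatase exemption turns on cause, so it says nothing about direction. No other section restates the lipid and glucose rule.

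**What the other rules repair.** The dose-reduction criterion acts independently of the exemptions.

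| Course of a Grade 3 or higher lipid or glucose event | As printed | Reworded |
|---|---|---|
| Leads to a dose reduction | DLT | DLT |
| Recovers, resumed at the same dose (e.g. Table 8, held 7 days or less) | DLT | exempt |
| Unresolved, treatment stopped without reduction (14-day limit, or Grade 4 hyperglycemia that stays unresolved) | not a DLT | DLT |
| Unresolved, managed without reduction | not a DLT | DLT |

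Only the last three rows are misclassified. Table 8 does not use CTCAE grades, so mapping its grades to Section 4.2 is approximate.

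**When a missed event also removes the patient.** This concerns only the third row. Planned doses are 1 sirolimus plus 2 Turalio per day (Section 9.7). The plan does not say whether the 80% is per drug or pooled. Nor does it fix the window: Section 4.2 points to the 56-day DLT period, while Section 4.1, for patients who stop for progression or unrelated death, applies the rule "after the end of the first cycle of treatment assessment and the patient received at least 80% of the planned doses", which suggests 28 days. All combinations are shown.

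*Both drugs stopped from day d* (Grade 4 hyperglycemia): fraction = (d − 1)/W, the same per drug or pooled.

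- W = 56: d = 45 gives 44/56 = 78.6%; d = 46 gives 45/56 = 80.4%.
- W = 28: d = 23 gives 22/28 = 78.6%; d = 24 gives 23/28 = 82.1%.

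*Sirolimus held from day h, Turalio continued for 14 days, then both stopped* (taking study treatment to mean both drugs). Per drug, sirolimus gives the same cut-offs as above: h = 45 (W = 56) and h = 23 (W = 28). Pooled fraction = [(h − 1) + 2(h + 13)]/(3W).

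- W = 56: h = 36 gives (35 + 98)/168 = 79.2%; h = 37 gives (36 + 100)/168 = 81.0%.
- W = 28: h = 14 gives (13 + 54)/84 = 79.8%; h = 15 gives (14 + 56)/84 = 83.3%.

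At or before these days the patient falls below 80%, has no DLT as printed, and is replaced. Holds that end in recovery are not in this set.

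**Scale of the underlying events.** 0.30 × 18 = 5.4, so at least about 5 of 18 patients would be expected to have each lipid event at some grade. The Grade 3 or higher share is not given.

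**Sensitivity of the design to one DLT.** Section 4.1's simulated trial (Figure 4) has 2, 3, 10 and 3 patients at levels 2 to 5, with one DLT at level 4 and two at level 5. The plan does not give the skeleton, so I assumed 0.124/0.250/0.398/0.542/0.666, with the empiric model, the stated normal prior (mean 0, variance 1.34) and full weights. This reproduces the plan's level 4 estimate of 18.6% (6%, 37%) and its choice of level 4.

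| Change | Level 4 estimate | Selected level |
|---|---|---|
| None | 18.6% | 4 |
| Remove one DLT | 11.8% to 13.4% | 5 |
| Add one DLT at level 2, 3, 4 or 5 | 23.8% to 29.3% | 4 |

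This shows that one reclassified event can move the dose in a trial of 18. It says nothing about what happened in this trial.

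**The case against.** The strongest reply is that nobody would have applied the literal sense. The bullet opens with the word For, unlike its neighbors, and reads naturally as a free-standing rule that these events are DLTs only if unresolved. Its place under the exemptions rests partly on indentation in the extracted text. That is a fair account of how the slip arose, and investigators may well have used the intended sense. But the text shows the bullet at the same level as the other three exemptions, and no other section gives the right direction, so a reader cannot tell which rule was used.

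Second, the affected set is narrow. If Table 9 is followed, a recovered Grade 3 lipid event is resumed one level lower and is a DLT under either wording. Over-counting therefore needs a departure from that guidance or Table 8's discretionary branch. This stands. The gaps for unresolved events remain.

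Third, Phase 1 is complete, and the DLT tally was not the only planned input to the dose, since Section 8.1 also weighs toxicities outside the DLT window. Both points are right, and they confine the value of the correction to reporting and to confirming the dose.

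Fourth, the 14-day limit is not absolute. Section 8.1 also mentions interruptions longer than three weeks, and the medical monitor may approve continuation beyond 14 days. A 21-day hold moves the pooled cut-offs from day 36 to 31 (56 days) and from day 14 to 12 (28 days). The illustration shifts; the conclusion does not.

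**Conclusion.** The concern holds. Followed as written, the exemption classifies controlled and uncontrolled lipid and glucose events in the opposite sense to the two comparable exemptions, and it feeds the Phase 1 primary outcome. The misclassification is limited to events that do not lead to a dose reduction, and it can bias the DLT rate in either direction. The number of such events, the reading applied, and any effect on dose level 3 cannot be determined from the documents. The evaluability days rest on the stated assumptions about the 80% basis and the hold limit, and the Figure 4 exercise on an assumed skeleton. Nothing here shows that dose level 3 is wrong. The correction should be made because the Phase 1 results will be reported against this definition.

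**What to change.** 1. Reword the bullet so that Grade 3 or higher hypercholesterolemia, hypertriglyceridemia or hyperglycemia is exempt when it resolves or is controlled with standard-of-care treatment, and is a DLT only if unresolved. Give a threshold for controlled.
2. State that discontinuation for such an unresolved event is a DLT, so that the patient is counted and not replaced.
3. State which reading was applied in Phase 1.
4. Check the 18 evaluable patients, and any who were replaced, for these events within 56 days.
5. Only if a classification changes, report the Section 13.3.1 DLT proportions and TITE-CRM estimates under the corrected rule, and say whether level 3 is still closest to 25%.

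The cost is a one-line amendment and a short review of laboratory and adverse event data, with a model re-run only if needed. The estimated DLT rates may move up or down. Events reduced under Table 8 or 9 stay DLTs through the dose-reduction criterion. If the intended reading was used, one sentence saying so settles most of the matter.

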**Handling of product specific AESIs (Adverse Events of Special Interest)**

All AESIs defined in the study protocol and noted below should be collected and be exchanged between the Parties within the process and timeframes outlined in the Section - Exchange of Safety Information from Investigator/Institution to DSI (please see below):

- AESI
  - Hepatic events (both serious and non-serious) which meet the potential Hy's Law criteria defined as an elevated (ALT and/or AST)  $\geq 3 \times$  ULN with simultaneous total bilirubin  $\geq 2 \times$  ULN, regardless if it is due to disease progression per Investigator assessment, that may occur at different time points during the study conduct, should always be reported to DSI.

#### **4.3 Number of Patients**

Approximately 43 evaluable patients are planned for enrollment.

**Phase I:** 18 patients  
**Phase II:** 25 patients

### **5. SUBJECT SELECTION AND WITHDRAWAL**

#### **5.1 Inclusion Criteria**

5.1.1. Disease site/type with pathologic confirmation of diagnosis at participating cancer site.

Note: If recurrence occurred greater than two years after resection, a biopsy to confirm recurrence should be performed and used for confirmation of diagnosis at the participating site.

Phase 1: Advanced, unresectable sarcoma (any subtype, except for patients with pigmented villonodular synovitis for which metastatic disease is required).  
Phase 2: Advanced, unresectable malignant peripheral nerve sheath tumors (MPNSTs)

5.1.2. Extent of disease  
Unresectable

5.1.3. Allowable prior therapy  
Phase 1: Progressed on standard of care therapy, if one is available.

**Columbia University Medical Center**  
**Herbert Irving Comprehensive Cancer Center**  
**Version Date: 04/21/2021**

Phase 2: MPNST with 0-3 prior cytotoxic systemic therapies (no prior radiotherapy is necessary).

5.1.4. ECOG performance status

0, 1, or 2

5.1.5. Age greater or equal to 18 years. Because no dosing or adverse event data are currently available on the use of Turalio® in combination with Sirolimus in patients <18 years of age, children are excluded from this study, but will be eligible for future pediatric trials.

5.1.6. Presence of measurable lesions by Response Evaluation Criteria in Solid Tumors (RECIST) v1.1

5.1.7. Allowable laboratory values with date range

- Labs should be done within 14 days of starting Cycle 1 Day 1 treatment
- ANC  $\geq 1.5 \times 10^9/L$ , Hgb  $> 10 \text{ g/dL}$ , and platelet count  $\geq 100 \times 10^9/L$
- AST/ALT/ALP/GGT  $\leq$  upper limit of normal (ULN)
- Total bilirubin and direct bilirubin  $\leq$  ULN
- Patients with hyperbilirubinemia clinically consistent with an inherited disorder of bilirubin metabolism (e.g., Gilbert syndrome) will be eligible at the discretion of the principal investigator if total bilirubin is  $\leq 1.5 \times$  ULN
- Albumin  $\geq 3.0 \text{ g/dL}$ .
- Creatinine  $\leq 1.5 \times$  ULN or calculated creatinine clearance (CrCl)  $> 60 \text{ mL/min}$  using the Cockcroft-Gault formula less than eight days prior to start of treatment.

5.1.8. Women of child-bearing potential must have a negative serum pregnancy test at screening and must agree to use an effective form of contraception from the time of the negative pregnancy test and for a minimum of 3 months after the last dose of study drug. Effective forms of contraception include abstinence, hormonal contraceptive (injectable or implantable) in conjunction with a barrier method, a double barrier method, diaphragm or cervical cap with a cream or gel that kills sperm, bilateral tubal occlusion, vasectomy, or an intrauterine device (IUD). Women of non-child-bearing potential must have been postmenopausal for  $\geq 1$  year or surgically sterile. The effects of Turalio® and Sirolimus on the developing human fetus are unknown. For this reason women of child-bearing potential and men must agree to use adequate contraception (hormonal or barrier method of birth control; abstinence) prior to study entry, for the duration of study participation and 3 months after completion of Turalio® and Sirolimus administration. Should a woman become pregnant or suspect she is pregnant while she or her partner is participating in this study, she should inform her treating physician immediately. Men treated or enrolled on this protocol must also agree to use adequate contraception prior to

**Columbia University Medical Center**  
**Herbert Irving Comprehensive Cancer Center**  
**Version Date: 04/21/2021**

the study, for the duration of study participation, and 3 months after completion of Turalio® and Sirolimus administration.

- 5.1.9. Fertile men must agree to use an effective method of birth control during the study and for up to 3 months after the last dose of study drug.
- 5.1.10. Willingness and ability to provide written informed consent prior to any study-related procedures and to comply with all study requirements.
- 5.1.11. For phase 2 specifically, agree to pre- and on-treatment tumor biopsies. If subject is unable to undergo paired research biopsies safely, subject may enroll onto the study without a research biopsy(ies) pending number of evaluable paired biopsies available at the discretion of the Principal Investigator.
- 5.1.12. Prior treatment-related AEs must be  $\leq$  grade 1 (CTCAE v4.0), except alopecia, at time of initiating study drug.

## **5.2      Exclusion Criteria**

- 5.2.1      Prior treatments –
  - i. Patients who have had systemic cytotoxic therapy or radiotherapy within 4 weeks (6 weeks for nitrosoureas or mitomycin C) or targeted therapy with small molecule inhibitors within 2 weeks prior to entering the study.
  - ii. Patients who have not recovered from adverse events ( $\leq$  grade 1; except alopecia) due to agents administered more than 4 weeks earlier.
  - iii. Patients need to be free of adverse effects ( $\leq$  grade 1; except alopecia) from prior treatments for at least 14 days from cycle 1 day 1 of Turalio® and Sirolimus.
- 5.2.2      Patients who are receiving any other investigational agents concurrently.
- 5.2.3      Concomitant treatment with other anti-neoplastic agents (hormonal therapy acceptable).
- 5.2.4      Patients with symptomatic brain metastases. Subjects with untreated brain metastasis  $\leq$  1 cm can be considered eligible if deemed asymptomatic by the investigator upon consultation with the medical monitor and do not require immediate radiation or steroids. Subjects with brain metastasis that is treated and stable for 1 month may be considered eligible if they are asymptomatic and on stable dose of steroids or if they do not require steroids following successful local therapy.

